## 4.2 Safety Endpoints Calculation Methods

### 4.2.1 Causality and Severity of AEs

An intensity, missing for an AE, will be imputed as severe. The summary of AEs by severity will use these imputed values, while the actual ones will be presented in the data listings.

An AE, whose relationship to treatment is missing, will be considered as related. These imputed values for causality will be used for the summary of AEs by relationship to treatment; the actual values will be presented in the data listings.

If the degree of missingness for the severity or relationship to study drug is >5%, then an additional table with non-imputed severity or causality will be provided.

Seriousness, outcome, and action taken, if missing for an AE, will not be imputed.

#### **4.2.2 Start and Stop dates, Time to Onset and Duration of AEs**

See section 9. for a complete description of handling of missing dates for AEs.

The analysis of the AEs will be based on the Safety Population (Section 4.3), i.e., will include all subjects who received the study treatment.

Time to onset of an AE will be computed in days using the formula: Time to onset = start date of AE – date of first vaccination. In case the time to onset of the AE is 0, i.e., the AE occurred the day of the first vaccination, the time to onset will be expressed in minutes. Time to onset relative to the second vaccination will also be reported in minutes, if an AE occurred the same day as the second vaccination.

Events that occur before vaccination will not be included in summaries but will be listed separately.

The duration of the AE will be reported in days and be computed as stop date of event – start date of event + 1.

#### **4.2.3 Causality and Severity of Local and Systemic Reactogenicity Events**

Local and systemic reactogenicity events are considered to be related to the treatment. Severity, when missing in a reported Local and Systemic Reactogenicity event, will not be imputed.

#### **4.2.4 Start and Stop dates, Time to Onset and Duration of Local and Systemic Reactogenicity Events**

For the analysis of solicited systemic and injection site reactions, missing dates will not be replaced. The analysis of the solicited symptoms based on the Safety Population (Section 4.3) will include only subjects with solicited systemic and injection site reactions, retrieved from the diary data.

The time to onset and duration of a specific local and systemic reactogenicity event will be calculated as defined above for an AE.

### 4.3 Safety Endpoints Population Analysis

All safety analyses will be based on the Safety Population, which will comprise all subjects having received at least one vaccine dose. The safety analyses will be performed by vaccine actually received at visit 1.

For the analyses of local and systemic reactogenicity events, the percentage in each table will be computed using the number of subjects having received the specified vaccination and who returned a diary card for the period of interest.

The safety analyses performed during the season 2018-2019 and 2019-2020 will be based on the subgroup of subjects from the safety set who were enrolled in the specific season.

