Title of the study: A pivotal, multicentre, randomized, modified double-blind, placebo-controlled phase 3 trial to assess the safety and clinical efficacy of M-001, an influenza vaccine administered intramuscularly twice in older adults and the elderly (≥ 50 years of age).	
EudraCT number: 2018-000468-27	Protocol code: BVX-010
ClinicalTrial.gov identifier: NCT03450915	
Sponsor: BiondVax Pharmaceuticals LTD, [name], Jerusalem, ISRAEL.	
Central Study Site: The trial will be conducted at approximately 85 institutions in Europe (including, but not limited to Bulgaria, Hungary, Poland, Ukraine, Latvia, Georgia and Croatia)	
Planned study duration: up to 2 years (2 consecutive flu seasons). It is designed to be completed after 2 influenza seasons unless stopped earlier or extended following recommendation of the DSMB. Subject participation duration: planned - up to 2 years.	Phase of Development: Phase III
Study population: Older adults and elderly (≥ 50 years of age). Randomization will be stratified by cohort and age of $<65>$. For season 2, randomization will also be stratified by participation (or not) to the sub-study. At least half of the participants will be ≥ 65 years old.	
Study design: A pivotal multicentre, randomized, modified double-blind, placebo-controlled study.	

Planned number of subjects:

Adaptive design (flexible enrolment); initially assumed to be 9,630 with an increase to 12,000 if the influenza attack rate in Season 1 is lower than expected. At least half of the participants will be ≥ 65 years of age at the time of the randomization.

Year 1 - cohort 1 (flu season 2018-2019): 4,055 subjects enrolled, as follows:

M-001: n = 2,027 (Lot #1, vials); Placebo: n = 2,028

Year 2 - cohort 2 (flu season 2019-2020): Approximately 8,000 subjects will be enrolled, as follows:

M-001: n = 4,000 (Lot#2, pre-filled syringes); Placebo: n = 4,000

PBMC (CMI) sub-study:

To assess the immune response to the vaccine, blood samples will be collected pre- and post-vaccination from a subset of 350 participants selected at random in pre-specified sites participating in Season 2. Approximately two hundred sixty three (263) will be selected from the M-001 group and 87 from the placebo group.

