11.5.1. Analysis Populations

The Safety Analysis population includes all subjects who received at least one dose of study vaccine. Subjects in the safety population will be analyzed according to the treatment actually received.

The intent-to-treat (ITT) population includes all subjects who received at least one dose of study vaccine. Subjects in the ITT population will be analyzed according to their randomization.

The per protocol (PP) population includes all subjects in the ITT subset satisfying the following criteria:

- Subject met all protocol-specified inclusion criteria and met no exclusion criterion,
- Subject received both doses of M-001/placebo as randomized, in the protocol-specified time frame, and at the intended dose level,
- Subject did not receive M-001/placebo that was not properly handled or was otherwise not acceptable for administration,
- Subject had at least one successful surveillance contact 15 days or more after the second dose of M-001/placebo, or attended at least one ILI visit due to ILI symptoms
- Subject did not receive a seasonal influenza vaccine between randomization and end of the surveillance period for Season 1,
- Subject did not receive a licensed live vaccine within 30 days of any dose of M-001/placebo, and
- Subject did not receive a licensed non-live vaccine within 21 days of any dose of M-001/placebo.

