### 4.4 Safety Endpoints Analysis

#### Local and Systemic Reactogenicity Events – Overall Summaries

Each set of tables described below will summarize the occurrence of events over the 3 following periods:

- P1. any day over 8-day period following first or second vaccination (Period = Day of the first/second vaccination to 7 days post first/second vaccination)
- P2. any day over 8-day period following first vaccination (Period = Day of the first vaccination to 7 days post first vaccination)
- P3. any day over 8-day period following second vaccination (Period = Day of the second vaccination to 7 days post second vaccination)

Summary of all the local and systemic reactogenicity **solicited** events provided for

- any local or systemic reactogenicity solicited events,
- any local events and by local event separately (5 events: blue spot/bruising, induration/swelling, redness/warmth, itching, pain/tenderness),
- any systemic reactogenicity events and by systemic reactogenicity event separately (14 events: decreased blood pressure/dizziness, chills/sweating, joint/muscle pain, headache, nasal congestion/runny nose/phlegm production/rhinitis, difficulty breathing/wheezing, general malaise/fatigue/loss of appetite, swelling/tender lymph nodes, irritability, rash, cough, sore throat, abdominal pain/diarrhea/nausea/vomiting, pruritus or itching on the body).

During the first season, fever was one of the solicited symptom and was graded subjectively as mild, moderate, or severe by the subject in addition to the oral body temperature daily record. This symptom was not recorded as such during the season 2019-2020. For homogeneity of reporting, oral body temperature daily records only will be presented for the 2 seasons and a separate table summarizing fever as a solicited symptom will be presented for season 2018-2019.

The tables will present the number and percentage of subjects with any events, the percentage in each table being computed using the number of subjects having received the specified vaccination and with diary data reported for local and systemic reactogenicity in the period of interest as defined in P1, P2, and P3.

For each of the above tables, the number and percentage of subjects will be tabulated by treatment.

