#### **Per-Protocol (PP) Set**

The primary efficacy analysis set (PP Set) will exclude

- Subjects who did not satisfy all protocol-specified inclusion criteria or met at least one exclusion criterion,
- Subjects who did not receive both doses of M-001/placebo as randomized,
- Subjects who did not receive M-001/placebo that was properly handled or was otherwise not acceptable for administration (unblinded subjects will be excluded),
- Subjects or their representative who were not contacted by the surveillance center, did not have any phone call, or any visit 15 days or more after second injection,

- Subjects who received a seasonal influenza vaccine between randomization and end of the surveillance period,
- Subjects who received a licensed live vaccine within 30 days of any dose of M-001/placebo that interfered with the evaluation of the investigational product, and
- Subjects who received a licensed non-live vaccine within 21 days of any dose of M-001/placebo that interfered with the evaluation of the investigational product.

Data from the database will be used to flag the protocol violations.

The results of the NP or nasal and throat swab collected outside of the allowed window following the ILI will be considered valid.

List of subjects excluded from the per-protocol analysis will be finalized prior to unblinding the database and described in the blinded data analysis memo.

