## 11. CHANGES OF ANALYSIS FROM PROTOCOL

Protocol version 1.0

No lot consistency analysis will be performed in a subset of subjects from Cohort 2, since all lots needed for the entire study will be produced by Cytovance. Immunogenicity analyses to be performed in a subset of subjects from Cohort 2 will be defined in a separate document (SAP for immunogenicity analyses).

Protocol version 5.0 – Amendment 1

The following changes were made compared to the analyses described in the protocol.

- the ILI episode for which a nasal or throat swab was collected outside of the allowed window of 3 days post onset date will be considered as a qRT-PCR or culture confirmed ILI if the results of the qRT-PCR or culture were positive. Review of each case will be performed prior to unblinding and documentation provided in the blinded data review meeting memo (see section 5.3).
- the analysis of the secondary efficacy assessment consisting in the between-group comparison of the number of days with respiratory or systemic symptoms among subjects with qRT-PCR- or culture-confirmed influenza illness will be performed on the percentage of subjects with number of days with respiratory or systemic symptoms in the following categories:
  - < 7days
  - At least 7 and < 14 days
  - At least 14 and < 21 days
  - > 21 days

Cochran-Mantel-Haenszel test with 4 strata corresponding to the combination of age category and cohort will be used.

- these exploratory endpoints have been added :
  - Reduction, due to vaccination with M-001, in the proportion of subjects with serious ILI with or without confirmation by viral culture or qRT-PCR analysis
  - Reduction, due to vaccination with M-001, in the proportion of subjects taking medications due to qRT-PCR- or culture-confirmed ILI

In addition, more details are provided in the SAP compared to the protocol.

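### Safety tables group subjects by the Visit 1 injection only, so events after a different product at Visit 2 are counted under the wrong product

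*SAP*

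**What the plan says.** Protocol 11.5.1 defines the safety population as everyone given at least one dose and states: "Subjects in the safety population will be analyzed according to the treatment actually received". It sets no limit to the first dose and has no rule for a subject who received both products.

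SAP 4.3 uses the same population but groups it differently: "The safety analyses will be performed by vaccine actually received at visit 1".

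SAP 4.4 reports reactogenicity over three periods: after either dose (P1), after dose 1 (P2) and after dose 2. The last is defined as "P3. any day over 8-day period following second vaccination". On grouping it adds: "For each of the above tables, the number and percentage of subjects will be tabulated by treatment". SAP 4.3 sets the denominator as "the number of subjects having received the specified vaccination and who returned a diary card for the period of interest", which depends on having had the injection and a diary, not on which product was injected.

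For efficacy, SAP 5.3 removes from the per-protocol set "Subjects who did not receive both doses of M-001/placebo as randomized". Those subjects stay in the safety population.

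SAP Section 11 introduces its list for protocol version 5.0 with "The following changes were made compared to the analyses described in the protocol". The Visit 1 rule is not in that list, nor in the summary of changes at the front of the SAP.

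**The concern.** An as-received analysis should credit an event to the product the subject had been exposed to. With two injections, a rule that looks only at the first ignores half of the planned exposure. It gives the right answer for a subject who had the same product twice, even if that was the wrong product both times. It fails when the Visit 2 product differs from the Visit 1 product.

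The grouping then feeds several outputs. SAP 4.2.3 treats reactogenicity events as related to treatment, so a reaction to a mis-given M-001 dose would appear as a related reaction under placebo. SAP 4.4 compares arms by chi-square for each vaccination and compares dose 1 with dose 2 within arm by McNemar's test. A mixed-product subject brings a change of product into a test meant to compare doses. The unsolicited AE, SAE, AESI and NOCI tables use the same grouping. Safety is a primary objective, and for rare events one misplaced case can change how a table reads.

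**Working it through.** The check is mainly of text. The plan states no figure that depends on this rule, so there is none to reproduce.

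**Step 1: apply the rule to each sequence.**

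- *Same product at both visits.* The Visit 1 rule and an as-received rule agree.
- *Placebo, then M-001.* The subject is in the placebo column throughout. Events before Visit 2 belong there. Reactions after dose 2 (in P3, and within P1) and later AEs, SAEs, AESIs and NOCIs follow M-001 exposure but are counted under placebo.
- *M-001, then placebo.* The subject is in the M-001 column throughout. Reactions to the placebo injection at dose 2 are counted under M-001 in P3. Later AEs, SAEs, AESIs and NOCIs also stay under M-001. That is reasonable, because the subject had already been exposed to it.

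**Step 2: look for a provision that regroups.** SAP 4.3 and 4.4 contain none. SAP 8.5 tabulates how many doses were received and the time between them, not which product was given at each, so the planned exposure tables would not reveal mixed dosing.

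**Step 3: illustrate the size for common reactions.** Inputs from the Protocol Synopsis: cohort 1 "M-001: n = 2,027 (Lot #1, vials); Placebo: n = 2,028", and 4,000 placebo subjects planned for cohort 2, so 2,028 + 4,000 = 6,028. The documents give neither a mis-dosing rate nor reaction rates. The values below are assumptions.

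Let m be the share of placebo subjects given M-001 at Visit 2, and p_P and p_V the true dose 2 reaction rates for placebo and M-001. Then

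observed placebo rate = (1 − m) × p_P + m × p_V, so the shift is m × (p_V − p_P).

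With p_P = 10%:

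| m | Subjects (m × 6,028) | Shift if p_V = 30% | Shift if p_V = 50% |
|---|---|---|---|
| 0.05% | 3 | 0.01 points | 0.02 points |
| 0.1% | 6 | 0.02 points | 0.04 points |
| 0.5% | 30 | 0.10 points | 0.20 points |
| 1% | 60 | 0.20 points | 0.40 points |

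For example, 0.5% × (30% − 10%) = 0.10 percentage points.

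**Step 4: rare events.** Suppose one SAE follows a mis-given M-001 dose, and the correct split is a + 1 on M-001 and b on placebo. The table shows a and b + 1. The between-arm difference goes from a + 1 − b to a − b − 1, a change of two events from one misplaced case.

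**The case against.** The strongest reply is that the SAP does not contradict the protocol. It keeps the as-received principle, does not revert to analysis as randomised, and adds a tie-break where the protocol is silent. Section 11 also closes by saying that the SAP gives more detail than the protocol. This stands in part: the accurate description is a narrowing. But a general remark about detail does not tell a reader that the second injection is disregarded.

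A reader might infer from the per-protocol exclusion that the plan expects placebo-then-M-001 subjects. It does not show that. The exclusion also covers a missed second dose, which the protocol anticipates, and the wrong product at both visits. Protocol 5.3.1, 5.3.2 and Section 6 point to a low rate: kits are matched centrally, packs are tied to one patient, an unblinded person prepares the syringe, and the two products look different.

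A reader might also infer that the rule works to hide harm. The documents do not support this. Misplacement runs both ways between the products. In P3 both sequences narrow the gap between arms only if M-001 is the more reactogenic product, and Protocol 2.3.1 describes AEs after M-001 as similar to those after placebo.

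Finally, SAEs and NOCIs are listed individually, deviations are listed, and the DSMB can ask for a subject to be unblinded. This helps, but no listing is stated to show the product given at each dose.

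**Conclusion.** The point holds as a defect of limited size. Followed literally, SAP 4.3 credits events after a different Visit 2 product to the wrong column, nothing elsewhere in the SAP corrects this, and the narrowing of the protocol rule is undeclared. A charge of direct conflict with the protocol goes too far, because the protocol does not address subjects given both products.

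The effect depends entirely on how many mixed-product subjects there are. The documents do not say; the number is probably very small and may be zero. Under the assumed rates, placebo dose 2 reaction rates move by 0.01 to 0.40 percentage points, which is negligible. What remains is the chance that a single rare event is misplaced. This is a desirable clarification and does not threaten the safety conclusions as a whole.

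**What to change.** Amend SAP 4.3 and 4.4 before unblinding:

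- Tabulate dose-specific reactogenicity (P2, P3), numerators and denominators alike, by the product received at that dose.
- For P1 and for the AE, SAE, AESI and NOCI tables, count events with onset after a first M-001 dose under M-001, and events before any M-001 exposure under placebo. Simply relabelling anyone with one M-001 dose as M-001 would not do, because it would move events from before that exposure into the M-001 column.
- State the denominators for these tables, since a placebo-then-M-001 subject can contribute to both columns, and footnote it.
- Exclude mixed-product subjects from the within-group McNemar comparison.
- List these subjects with the product given at each dose.
- Record the rule in SAP Section 11.

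The cost is a short paragraph, some programming and one listing, with no new data beyond the product given at each visit. If no subject had mixed dosing, no result changes. If any did, the rule will have been set in advance.

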### 4.4 Safety Endpoints Analysis

#### Local and Systemic Reactogenicity Events – Overall Summaries

Each set of tables described below will summarize the occurrence of events over the 3 following periods:

- P1. any day over 8-day period following first or second vaccination (Period = Day of the first/second vaccination to 7 days post first/second vaccination)
- P2. any day over 8-day period following first vaccination (Period = Day of the first vaccination to 7 days post first vaccination)
- P3. any day over 8-day period following second vaccination (Period = Day of the second vaccination to 7 days post second vaccination)

Summary of all the local and systemic reactogenicity **solicited** events provided for

- any local or systemic reactogenicity solicited events,
- any local events and by local event separately (5 events: blue spot/bruising, induration/swelling, redness/warmth, itching, pain/tenderness),
- any systemic reactogenicity events and by systemic reactogenicity event separately (14 events: decreased blood pressure/dizziness, chills/sweating, joint/muscle pain, headache, nasal congestion/runny nose/phlegm production/rhinitis, difficulty breathing/wheezing, general malaise/fatigue/loss of appetite, swelling/tender lymph nodes, irritability, rash, cough, sore throat, abdominal pain/diarrhea/nausea/vomiting, pruritus or itching on the body).

During the first season, fever was one of the solicited symptom and was graded subjectively as mild, moderate, or severe by the subject in addition to the oral body temperature daily record. This symptom was not recorded as such during the season 2019-2020. For homogeneity of reporting, oral body temperature daily records only will be presented for the 2 seasons and a separate table summarizing fever as a solicited symptom will be presented for season 2018-2019.

The tables will present the number and percentage of subjects with any events, the percentage in each table being computed using the number of subjects having received the specified vaccination and with diary data reported for local and systemic reactogenicity in the period of interest as defined in P1, P2, and P3.

For each of the above tables, the number and percentage of subjects will be tabulated by treatment.

The percentage of subjects with any local or systemic reactogenicity solicited events overall and by vaccination will be compared between the groups using the chi-square test. Within-group comparison between the percentage of subjects with any local or systemic reactogenicity solicited events after first and second vaccination will be performed using Mc Nemar test.

Descriptive tables for duration of event will also be provided by solicited event.

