Physical Examination: On Visit 1 standard physical examination should be performed prior to the first study vaccination, but if subject's medical history is known based on medical records, a limited, targeted physical examination may be performed instead of standard scope PE prior to the first study vaccination by a study clinician, however in any case neurologic component of PE and physical examination of head/upper respiratory tract must be performed. On visits other than 1 limited, targeted physical examination may be performed if assessed by investigator as needed.

Reactogenicity Assessments: This will include an assessment of solicited events occurring from the time of each M-001 study vaccination [Day 0 (Visit 1), Day 22 (Visit 2)] through 8 days after the study vaccination (inclusive of vaccination day), which includes an assessment of systemic reactions (Fever; Decreased blood pressure and/or dizziness; Chills and/or sweating; Joint and/or muscle pain; Headache; Nasal congestion, runny nose, phlegm production, rhinitis; Problems with breathing (difficulty breathing, wheezing); General malaise, fatigue, loss of appetite; Itching on body/ pruritus; Swelling/tender lymph nodes; Irritability; Rash; Cough; Sore throat; Stomach problems (abdominal pain, diarrhea, nausea, vomiting)) and local – injection site reactions (Blue spot/ bruising; Induration / Swelling; Redness / Warmth; Itching), Pain/ tenderness

Memory Aids: All subjects will complete a subject memory aid (paper diary) from the time of each study vaccination [Day 0 (Visit 1), Day 22 (Visit 2)] through 8 days after the study vaccination (study vaccination day inclusive). Subject memory aids will be reviewed with the subject for AEs at the site visit following the first study injection, and over the phone after the second study

injection (unless the subject comes to the site for Visit 3). If a subject noted ongoing injection site or systemic reactogenicity on the 7th day following the study injection day, the memory aid will continue to be completed and reviewed until resolved. Subjects will be requested to deliver memory aids filled in after the second vaccination when completed – to the site.

Questionnaires: information on ILI clinical presentation, duration etc. will be collected in the study by study personnel.

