9. ASSESSMENT OF SAFETY

9.1. Specification of Safety Parameters

Safety will be assessed by the frequency and severity of:

1. SAEs and NOCIs occurring from the time of the first study vaccination through subjects' participation in the trial.
2. Solicited events – reactogenicity events occurring on the day of each study vaccination through 8 days* after each study vaccination:
**Vaccination day is considered Day 0, with 7 days following (8 days in total)*
 - a) Injection site reactions including pruritus, ecchymosis, erythema, warmth, induration, swelling, pain and tenderness.
 - b) Systemic reactions including fever, feverishness, general malaise, fatigue, loss of appetite, myalgia or arthralgia, decreased blood pressure or dizziness, chills and/or sweating, nasal congestion, runny nose, phlegm production, rhinitis, problems with breathing (difficulty breathing, wheezing), itching on body/ pruritus, swelling/tender lymph nodes, irritability, rash, cough, sore throat, headache and stomach problems (abdominal pain, diarrhea, nausea, vomiting).
3. Unsolicited AEs/SAEs – unsolicited AEs/SAEs occurring from the time of the study vaccination through approximately 22 days after each study vaccination (day of the vaccination inclusive) .

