Ecchymosis (Bruising)*	Does not interfere with daily activity	Interferes with daily activity	Prevents daily activity
Erythema (Redness)*	Does not interfere with daily activity	Interferes with daily activity	Prevents daily activity
Induration (Hardness)/Swelling*	Does not interfere with daily activity	Interferes with daily activity	Prevents daily activity

* Will be also measured in mm but size will not be used as criterion for stopping the trial

Ecchymosis, erythema, and induration /swelling as analyzed by measurement will be graded as follows:

Table 6: Injection Site Reactogenicity Measurements

Injection Site Reaction	Small	Medium	Large
Ecchymosis *	<20 mm	20 mm – 50 mm	>50 mm
Erythema*	<20 mm	20 mm – 50 mm	>50 mm
Induration /Swelling*	<20 mm	20 mm – 50 mm	>50 mm

* Will not be used as criterion for stopping the trial.

Table 7: Subjective Systemic Reactogenicity Grading

Systemic (Subjective)	Mild (Grade 1)	Moderate (Grade 2)	Severe (Grade 3)
Feverishness (Chills/Shivering/Sweating)	No interference with daily activity	Nonsignificant interference with daily activity	Significant interference, prevents daily activity
Fatigue (Tiredness)	No interference with daily activity	Nonsignificant interference with daily activity	Significant interference, prevents daily activity
Malaise (General Unwell Feeling)	No interference with daily activity	Nonsignificant interference with daily activity	Significant interference, prevents daily activity

Systemic (Subjective)	Mild (Grade 1)	Moderate (Grade 2)	Severe (Grade 3)
Myalgia (Body Aches/Muscular Pain)*	No interference with daily activity	Nonsignificant interference with daily activity	Significant interference, prevents daily activity
Arthralgia (Joint Pain)*	No interference with daily activity	Nonsignificant interference with daily activity	Significant interference, prevents daily activity
Headache	No interference with daily activity	Nonsignificant interference with daily activity	Significant interference, prevents daily activity
Nausea	No interference with daily activity	Nonsignificant interference with daily activity	Significant interference, prevents daily activity

* Not at injection site.

Oral temperature[#] will be graded as follows:

Table 8: Quantitative Systemic Reactogenicity Grading^{20,21}

Systemic (Quantitative)	Mild (Grade 1)	Moderate (Grade 2)	Severe (Grade 3)
(Age <60) Fever* - oral [†]	38.0°C – 38.4°C	38.5°C – 38.9°C	>38.9°C
(Age 60+) Fever* - oral [†]	37.3°C – 37.7°C	37.8°C – 38.2°C	>38.2°C

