## **OVERVIEW AND SUMMARY OF CHANGES FROM STATISTICAL ANALYSIS PLAN FINAL 1.0 DATED 17 DECEMBER 2018**

The SAP version 1.0 approved on December 17, 2018 is updated to version 2.0

- to incorporate changes made to the protocol through the current version 5.0 - Amendment 1.0 of the protocol,
- to add analyses missing in SAP version 1.0 to be in line with the protocol,
- to describe some conventions following a blinded data review meeting that took place after the end of flu season 2018-2019,
- to clarify one exploratory endpoint, add 2 exploratory endpoints and 2 sensitivity analyses, and
- to incorporate some editorial changes.

Updates to the SAP version 1.0 related to protocol amendment concern:

- the change to the study design with the addition of a second cohort to reach a total of ~12,000 subjects in the study. The second cohort is evaluated during the flu season 2019-2020 while cohort 1 was evaluated during the flu season 2018-2019 (section 3.4). In addition, no subject was participating in two consecutive flu seasons.
- the removal of the long-term efficacy assessment over a second influenza season from the list of secondary objectives. All efficacy and safety analyses related to second flu season were removed from SAP version 1.0 (section 2.2).
- the addition of an immunogenicity objective (section 2.2) and immunogenicity endpoints in section 6.
- the removal of the exploratory objective 2. in SAP version 1.0 concerning the assessment of incidence of clinic visits associated with the ILI episode
- the presentation of safety and efficacy results by cohort (cohort 1 and 2, corresponding to flu season 2018-2019 and 2019-2020, respectively)
- the removal of fever from the list of solicited symptoms. Presence/absence of fever will be evaluated using the reported temperature by the subject (Section 4.1)

The following updates were made to the first version of SAP to be in line with the protocol version 5.0 (these analyses were missing from SAP version 1.0 but are described in the protocol):

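### The SAP's any-systemic and any-solicited reactogenicity composites omit fever, which the protocol lists as a solicited systemic reaction, so each arm's composite rate can only be too low

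*SAP*

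**What the plan says.** **Protocol v5.0.** Solicited local and systemic reactogenicity within 8 days of each dose is a primary safety objective and outcome (sections 3.1.1 and 3.2.1). Section 8.1 specifies an "assessment of systemic reactions (Fever; Decreased blood pressure and/or dizziness; Chills and/or sweating" and twelve more items. Section 9.1 agrees: "Systemic reactions including fever, feverishness, general malaise, fatigue" and others. In section 9.2.2, Table 8, titled "Quantitative Systemic Reactogenicity Grading", grades oral temperature by age. Section 11.5.2 asks for the proportion of subjects with each symptom, with any injection-site symptom and with any systemic symptom. It makes no exception for fever.

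**SAP v2.0.** Section 4.4 plans summaries for any local or systemic solicited event, for any of five local events, and for "any systemic reactogenicity events and by systemic reactogenicity event separately (14 events: decreased blood pressure/dizziness, chills/sweating" and the rest of a list without fever. It then states: "The percentage of subjects with any local or systemic reactogenicity solicited events overall and by vaccination will be compared between the groups". That comparison is by chi-square, with a McNemar test of dose 1 against dose 2 within each group.

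Temperature is handled apart from this. Section 4.4 defines fever from the recorded oral temperature (at least 38.0 °C under age 60, at least 37.3 °C from age 60), grades it in Table 3, and gives it its own chi-square and McNemar tests. The subjective fever item, collected only in 2018–2019, gets a separate table for that season.

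The SAP's overview of changes includes "the removal of fever from the list of solicited symptoms" among updates that follow from the protocol amendment. Section 4.1 still names fever as a solicited systemic reaction for the first season. Section 11, on departures from protocol v5.0, does not mention fever.

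**The concern.** A composite labelled any systemic reaction is normally read as covering every systemic reaction the protocol solicits. Here it does not, and the missing item is the one that is measured rather than self-rated. The any-local-or-systemic composite carries the between-arm and between-dose tests, and the overview of solicited events (Table 14.2.15.1) is marked for top-line reporting.

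The SAP's reason for separate reporting is homogeneity across seasons, because the subjective fever item was not recorded in 2019–2020. That justifies replacing subjective fever with measured fever. It does not justify leaving fever out of the composite, since daily oral temperature was recorded in both seasons and the SAP already has one definition and one grading for both.

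At stake is whether a summary of a primary safety outcome means what the protocol says it means, and whether the departure is traceable.

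**Working it through.** **1. Reproduce the SAP's count.** The section 4.4 list runs: blood pressure/dizziness; chills/sweating; joint/muscle pain; headache; nasal symptoms; breathing difficulty; malaise group; lymph nodes; irritability; rash; cough; sore throat; stomach group; itching on the body. That is 14, as stated.

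**2. Match it to protocol section 8.1.** The protocol list has 15 items. Fourteen pair one-to-one with the SAP list. The unpaired item is fever: 15 − 14 = 1.

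**3. Look for a route back.** No SAP section feeds the temperature-defined fever result into either composite.

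**4. Score a fever-only subject.**
- As planned: 0 of 14 systemic and 0 of 5 local, so classed as no reaction in both composites.
- With fever included: 1 of 15 systemic, so classed as a reaction in both.

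**5. Can the reader rebuild the protocol's rate?** Let *a* be the proportion with any of the 14 items, *f* the proportion with fever, and *b* the proportion with both. The protocol's rate is *a* + *f* − *b*. The planned tables give *a* and *f* but not *b*, so the rate is known only to lie between max(*a*, *f*) and *a* + *f*.

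**6. Direction.** The shortfall in each arm is *f* − *b*, which cannot be negative. The between-arm difference changes by the vaccine shortfall minus the placebo shortfall, which can have either sign.

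**7. Size, by assumption only.** The documents give neither *f* nor *b*. Suppose 1–5% of an arm reach the fever threshold and 20–50% of those report no other systemic item. With 6,000 per arm (protocol section 4):
- low end: 1% × 20% = 0.2%; 6,000 × 0.2% = 12 subjects
- high end: 5% × 50% = 2.5%; 6,000 × 2.5% = 150 subjects

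This is the effect on any systemic. To change any local or systemic, the variable named in the tests, a subject must also have none of the five local reactions, so the number there can only be equal or smaller.

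**8. Documentation.** The overview attributes the removal to the protocol amendment, but protocol v5.0 keeps fever in sections 8.1, 9.1 and 9.2.2. SAP section 4.1 keeps it for season 1, while the 14-item list leaves it out for both seasons. SAP section 11 is silent.

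**The case against.** The strongest reply is that fever is fully visible elsewhere. Measured fever has its own rate over the same 8-day periods, its own grades, and its own between-arm and between-dose tests, undiluted by 14 other symptoms. Table 14.2.16.1 on recorded temperature is also marked top-line. A severe-grade temperature must be recorded as an adverse event as well (protocol section 9.2.2, SAP section 4.1), and the first set of SAP adverse-event tables includes such events. The overview announces the change and says fever will be judged from recorded temperature. The primary outcome is the occurrence of solicited events, not a composite, and the SAP attaches no success criterion or error rate to the composite.

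All of that stands, and it rules out several stronger readings a reader might infer. Fever has not been dropped from the safety report. A vaccine effect appearing mainly as fever would miss the composite test but would reach the temperature test. An isolated Grade 3 temperature does not disappear. Nor does a lower rate in each arm imply a bias in the vaccine's favour, because the direction of any change in the between-arm difference is unknown.

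The reply does not restore the protocol's any-systemic summary, because separate marginal tables cannot give the combined rate (working, step 5). The separate tables are also less detailed: the composite overview is tabulated by age group (Tables 14.2.15.16 to 14.2.15.18), while none of Tables 14.2.16.1 to 14.2.16.6 is, although the fever threshold depends on age.

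**Conclusion.** The point holds as a mismatch between protocol and SAP in how the composites are built, together with a documentation error. Both composites understate, or at best equal, the rate the protocol describes, in both arms and both seasons. The amount cannot be computed from the documents. The 12 to 150 subjects per arm rest wholly on assumed fever and fever-only rates and apply to any systemic. The true figure may be small, because fever often comes with chills or malaise, which do count.

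This is a should-fix. Treating it as critical would require fever to be hidden or untested, and the SAP shows that it is neither.

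**What to change.** In SAP section 4.4, for both seasons:

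- Count temperature-defined fever, by the SAP's existing age-specific definition, as the fifteenth component of any systemic and as a component of any local or systemic. Run the planned chi-square and McNemar tests on that composite.
- Use the SAP Table 3 grade as the fever component's severity in the maximum-severity summaries, with a note that it is a measured grade while the other items are subject-rated.
- Treat a missing temperature as other missing diary responses are treated in SAP section 9.2, that is, as no event.
- Keep the separate temperature tables and the season 1 subjective-fever table.

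In the overview, correct the attribution to the protocol amendment. List any departure that remains in SAP section 11, and bring section 4.1 into line.

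The cost is one derivation from data already collected, plus wording. No visit, data item or sample-size change is needed. The downside for the sponsor is a reactogenicity rate that may be slightly less favourable.
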